We will document recruitment rates (i.e., percent of those offered participation in the study who sign up), as well as study retention rates, to assess appropriateness of follow-up procedures. Demand for the chatbot will be measured as: 1) number of texts to the chatbot; and 2) engagement at repeated administrations (if randomly assigned to this condition).

To validate receipt of treatment, a study team member will contact a random subset of participants (i.e., approximately 10%) who reported engaging in some kind of treatment to solicit additional details on their service use and experience through phone/Zoom call or online questionnaire, which will provide additional validation, and when possible, participants will also be asked to provide some kind of documentation for the services they reported using (e.g., send receipt of therapy session or provide email indicating they signed up for a recommended online program).

Participants will receive invitation and reminders via email, phone, and/or text message for each assessment, and if they have not completed the conversation with the chatbot. Participants may receive thank you messages for completing assessments.

PHI discussions via email will use WashU guidelines: 1) a test email will be sent to the participant to verify their identify (confirm correct recipient) and that this email will be sent in a secure manner (i.e., [secure] in subject line); 2) The body of the email will instruct the participant to send all information as a response to this thread and to not remove the "[secure]" from the subject line; 3) document in our research records the participant's agreement to provide information over email.

E2. Subject Selection and Withdrawal

E2.A. Inclusion Criteria

U.S. resident; English-speaking; age 18 years or older; own a smartphone; screen positive for a DSM-5 clinical or subclinical eating disorder; not receiving treatment for an eating disorder

E2.B. Exclusion Criteria

We will exclude participants who are currently receiving treatment for an eating disorder given the goal to increase access to services for those not receiving help. In addition, we do not plan on enrolling individuals who screen for Avoidant Restrictive Food Intake Disorder.

E2.C. Ethical Considerations

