All key personnel involved in the design or conduct of research involving human subjects will receive the required education on the protection of human research participants prior to the start of the study. Participants will be informed that they do not have to answer any questions that make them uncomfortable. There are minimal risks for participating in testing.

Participants will be provided with the contact information of the research staff. As a clinical psychologist, the PI is trained in how to address safety issues. If any participant appears to be in crisis, they will be given information to call emergency services and will be notified that the chatbot is not designed to provide crisis support. Any adverse event will be reported promptly to the mentorship team, the NIH, and the IRB.

Confidentiality: Participant confidentiality will be maintained in compliance with HIPAA privacy protected servers. Study IDs will be linked with participant names, email addresses, and phone numbers in a separate password-protected file stored on a secure, password-protected server that only key study personnel have access to. All employees of the study with access to protected health information (PHI) are required to complete HIPAA training and comply with the privacy procedures in place at Washington University.

X2AI (x2ai.com), our chatbot collaborator, is a HIPAA-compliant mental health chatbot company with a dedicated and talented team of software engineers who are experienced in building chatbots that support mental health. X2AI will host the proposed chatbot and all data collected within the chatbot. X2AI will comply with the rules regarding handling of PHI under HIPAA.

Adverse Events: For the purpose of this study, adverse events will be defined as unanticipated problems involving risks to the study participants. A serious adverse event will be defined as any untoward occurrence that results in death, is life-threatening, or creates persistent and significant disability. The PI will consult with mentors to identify serious adverse events. Any potentially adverse events will be evaluated by the PI within 72 hours. All serious adverse events will be immediately reported to the IRB. All adverse events and study withdrawals, together with a detailed explanation of the event and withdrawal, will be provided to the mentorship team.

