ı					

F3. Data Collection and Reporting Procedures for Adverse Events

For the purpose of this study, adverse events will be defined as unanticipated problems involving risks to the study participants. A serious adverse event will be defined as any untoward occurrence that results in death, is life-threatening, or creates persistent and significant disability. The PI will consult with mentors to identify serious adverse events. Any potentially adverse events will be evaluated by the PI within 72 hours. All serious adverse events will be immediately reported to the IRB. All adverse events and study withdrawals, together with a detailed explanation of the event and withdrawal, will be provided to the mentorship team.

F4. Study Outcome Measurements and Ascertainment

The goal is to determine the feasibility of delivering the chatbot and to generate data on the effect of the chatbot components on motivation for treatment and mental health services use. We will also explore if the chatbot components interact to predict outcomes. Data will inform developing an optimized chatbot, which we will test in a subsequent R01 trial.

The goal of this optimization trial is to inform an R01 randomized controlled trial of an optimized chatbot vs. a control condition. We will achieve that goal by evaluating feasibility and generating effect sizes of each component on outcomes, which will inform which components to retain in the optimized chatbot and be used to power a subsequent R01 trial.

G. Data Handling and Record Keeping

G1. Confidentiality and Security

Participant confidentiality will be maintained in compliance with HIPAA privacy protected servers. Study IDs will be linked with participant names and email addresses in a separate password-protected file stored on a secure, password-protected server that only key study personnel have access to. All employees of the study with access to protected health information (PHI) are required to complete HIPAA training and comply with the privacy procedures in place at Washington University.

X2AI (x2ai.com) is a HIPAA-compliant mental health chatbot company with a dedicated and talented team of software engineers who are experienced with building chatbots focused on supporting mental health. X2AI will host the proposed chatbot and all data collected within the chatbot. X2AI and Washington University are in a Business Associate agreement. X2AI will comply with the rules on handling of PHI under HIPAA.

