Training: All staff personnel are trained and comply with HIPAA regulations. All study team members will complete the CITI training and Good Clinical Practice training.

Performance Monitoring: The Data and Safety Monitoring Plan for this trial includes close monitoring by the PI and her mentoring team. Any adverse event will be reported promptly to the NIH and to the IRB.

H. Study Administration

H.1. Funding Source and Conflicts of Interest

This study is funded by NIH. Any potential financial conflicts of interest for individual research team members are reported according to the IRB requirements and procedures.

H.2. Participant Payment

Participants will receive a \$5 electronic gift card for completion of the baseline assessment, a \$10 electronic gift card for completion of the 2 week assessment, a \$10 electronic gift card for completion of the 6 week assessment, and a \$20 electronic gift card for completion of the 14 week assessment.

H.3. Study Timeline

As detailed in the table below, recruitment and enrollment for the randomized pilot trial (Study 2) will begin in the middle of Year 2. It is anticipated that enrollment will continue for one year, into the middle of Year 3. All enrolled participants will receive access to chatbot designed to facilitate health care utilization. Engagement with the chatbot will occur for up to approximately 2 weeks. Participants will complete a baseline assessment, and follow up assessments about 2 weeks, 6 weeks, and 14 weeks after baseline completion.

		Year 1		Year 2		Year 3		Year 4	
Study	Activity	1-	7-	13-	19-	25-	31-	37-	43-
		6	12	18	24	30	36	42	48
	Recruit and enroll participants				X	X			
Study 2:	Deliver the chatbot				X	X			
Randomized Optimization	Conduct follow-up assessments				X	Х	Х		
Trial	Analyze data and write-up						X	Х	
	Write and submit NIH R01 grant					Х	Х	X	X

I. References

- 2. Hay P. A systematic review of evidence for psychological treatments in eating disorders: 2005-2012. Int J Eat Disord. 2013;46(5):462-9. PMID: 23658093.

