- 39. Nielsen J. The usability engineering life cycle. Computer. 1992;25(3):12-22.

PART II: STATISTICAL ANALYSIS PLAN

Statistical Analysis Plan

Data will be analyzed using R version 4.2.1.

Primary Outcome: Chabot Component Effects on Self-Reported Receipt of Treatment and/or Services Utilization

Analyses will be executed using discrete time survival analysis and will reflect the proportional increase in odds of treatment and/or services utilization corresponding to receiving each chatbot component (motivational interviewing, psychoeducation, personalized recommendations, repeated administration). This approach estimates the effect of independent variables (i.e., chatbot components) on the occurrence of an event (i.e., treatment utilization). Models will be fit with treatment use regressed on follow-up time (2-week, 6-week, or 14-week) and each chatbot component. Models will not incorporate an intercept; this allows for estimation of treatment utilization odds among participants who have yet to report seeking treatment. The model will be estimated using a logit link, and for all coefficients, odds ratios and 95% confidence intervals will be computed. Parameters of primary interest include the time effects, which reflect odds of treatment seeking at each time point, as well as the main effects of each chatbot component. Censoring and missing data were accommodated using maximum likelihood estimation.

Primary Outcome: Time Effect on Help-Seeking Attitudes (Motivation and Willingness to Change and Seek Help)

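### The serious adverse event definition omits hospital admission and the services endpoint has no stated limit by setting or reason, so a non-life-threatening admission for deterioration can count as a favourable primary event without being classed as serious

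*Combined protocol and SAP*

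**What the plan says.** **Serious events.** Protocol E2.C and F3 use identical wording: "A serious adverse event will be defined as any untoward occurrence that results in death, is life-threatening, or creates persistent and significant disability". Mentors are consulted in identifying such events, and these go to the IRB immediately.

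**Other adverse events.** In the same two sections, "adverse events will be defined as unanticipated problems involving risks to the study participants". For these, "Any potentially adverse events will be evaluated by the PI within 72 hours". Section G1 (Performance Monitoring) adds: "Any adverse event will be reported promptly to the NIH and to the IRB". E2.C has a similar rule that also names the mentorship team.

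**Primary outcome.** The SAP heading is "Component Effects on Self-Reported Receipt of Treatment and/or Services Utilization". The estimates "will reflect the proportional increase in odds of treatment and/or services utilization corresponding to receiving each chatbot component". Protocol E1 describes the people eligible for the roughly 10% validation contact as those "who reported engaging in some kind of treatment". The F2 schedule refers to mental health services use questions but does not reproduce them.

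**Crisis.** E2.C states: "If any participant appears to be in crisis, they will be given information to call emergency services". Neither document says whether care that follows counts towards the primary outcome.

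**Use of the results.** F4 says that component effect sizes will decide which components are kept and will be used to power the later R01 trial.

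**The concern.** In most trials an emergency admission is plainly a bad outcome. Here the desired outcome is contact with services, so a possible harm and the hoped-for benefit can be the same observation. Suppose a participant's eating disorder or mood worsens after using the chatbot and she is admitted, without the event being life-threatening or leaving lasting disability. If she answers yes to the services question, she is an event in favour of whichever components she received. Under the written definition she is not a serious adverse event.

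Two things are at stake. One is safety capture: the admission is not automatically classed as serious and does not trigger the immediate report to the IRB. The other is the reading of the primary outcome, because the effect sizes that select components for the R01 could include some crisis care alongside planned help-seeking, and the planned analysis has no means of separating the two.

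**Working it through.** The plan states no figure on this point, so there is none to reproduce. The check is a comparison of texts, followed by an illustration of size.

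**1. Is admission covered elsewhere in the serious event definition?** No. E2.C and F3 carry the same three limbs (death, threat to life, persistent and significant disability), and no other section adds to them.

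**2. Would an admission be caught as an ordinary adverse event?** Possibly. The test is whether the problem was unanticipated. The Psychological Risks paragraph under E2.E already foresees that the chatbot may heighten some users' focus on their symptoms, and the abstract (B1) describes eating disorders as carrying high morbidity and mortality. Deterioration could therefore be judged anticipated and left out. The rule that adverse events go promptly to the NIH and IRB operates only once an event has been classed as one.

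**3. How would the team learn of it?** The F2 schedule contains no adverse event query. Assessments are online, so an admission may surface only as an answer to the services question. The validation contact covers about 10% of those reporting treatment and aims to confirm receipt. If k admissions are reported, the chance that at least one falls in that sample is 1 − 0.9^k: 10% for k = 1, 27% for k = 3, 41% for k = 5 and 65% for k = 10.

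**4. Does any planned analysis separate harm from benefit?** No. EDE-Q, PHQ-9 and GAD-7 are collected at follow-up, but the SAP analyses none of them and has no safety table. The help-seeking attitudes analysis drops anyone who reports seeking treatment at any follow-up, so a participant whose admission is coded that way leaves that analysis too.

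**5. How far could the primary estimate move?** Inputs:
- From the documents: about 200 participants (E2.D) and two levels per component, so 200/2 = 100 per level.
- Assumed, because the documents give neither: planned uptake of 10%, 20% or 30%, equal at both levels; and x crisis-only admissions, all at the yes level, in people who would otherwise report no care.

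With b planned users per 100 and a = b + x, the crude odds ratio is [a/(100 − a)] / [b/(100 − b)]. The standard error of its log is √(1/a + 1/(100 − a) + 1/b + 1/(100 − b)).

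| Extra admissions at yes level | Uptake 10% | Uptake 20% | Uptake 30% |
|---|---|---|---|
| 2 | 1.23 | 1.13 | 1.10 |
| 5 | 1.59 | 1.33 | 1.26 |
| 10 | 2.25 | 1.71 | 1.56 |

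For 20% uptake and five admissions:
- Odds ratio = (25/75)/(20/80) = 0.333/0.250 = 1.33, and ln 1.333 = 0.288.
- SE = √(1/25 + 1/75 + 1/20 + 1/80) = √0.1158 = 0.340.
- 95% CI = exp(0.288 ± 1.96 × 0.340) = 0.68 to 2.60; z = 0.845, p about 0.40.

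**6. How many would it take to meet the SAP's p ≤ .05 threshold alone?** On the same 20% base:
- 32/100 v 20/100: OR = (32/68)/(20/80) = 1.88, SE 0.329, z = 1.92, p about 0.055.
- 33/100 v 20/100: OR = (33/67)/(20/80) = 1.97, SE 0.328, z = 2.07, p about 0.04.

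So about 13 extra crisis-only admissions per 100 would be needed. These are crude two-proportion figures. The planned discrete-time model adjusts for time and the other components and would differ somewhat.

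**The case against.** A reader might infer that an emergency admission always scores as success and never as harm. The documents do not support that, for four reasons.

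- A life-threatening admission is already a serious adverse event. Another admission can be an adverse event, evaluated within 72 hours and reported promptly to the NIH and IRB. What is lost is automatic classification as serious and the immediate report, not every route to a safety report.
- Endpoint event and adverse event are not exclusive. One admission can be recorded as both.
- The services items are not shown. The protocol speaks of mental health services, so a purely medical admission might not count, and the items may already record type or setting. Nor is inpatient care necessarily misclassified as treatment in a trial that targets a treatment gap.
- The numerical effect rests on assumed rates. About 13 crisis-only admissions per 100 caused by one component is hard to credit for a chatbot used for 5 to 20 minutes per E1 and rated minimal risk by the protocol.

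All four stand, and they limit the point to what can happen under the plan as written. They do not supply the missing limb of the definition, settle whether foreseeable deterioration is unanticipated, say which services count, or provide a safety analysis. The scales that could show deterioration are collected, but the SAP has no use for them. The last objection concerns significance; F4 uses the effect sizes themselves, and smaller numbers move those.

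**Conclusion.** The point holds in this form. The serious event definition omits hospital admission in both places, the adverse event definition turns on the word unanticipated, and the primary outcome has no stated limit by setting or reason. With no scheduled adverse event query and no safety analysis, a non-life-threatening admission for deterioration can count as a favourable primary event without being classed as serious or reported immediately to the IRB. It may still reach the NIH and IRB as an ordinary adverse event.

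The size is unknown. Under the assumptions shown, two to five extra admissions at one component level give odds ratios between 1.10 and 1.59 where the true effect on planned care is nil. A few such events would shift the effect sizes used to choose components and power the R01, but would be unlikely on their own to reach p ≤ .05. The change should be made because it is cheap and improves both safety capture and the reading of the primary outcome. Nothing in the documents shows that a wrong component would be selected.

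**What to change.** 1. **Protocol E2.C and F3:** add unplanned hospital admission to the serious adverse event definition, in the same words in both places. Emergency attendance without admission should be tabulated (item 3), not automatically made a serious event.
2. **Follow-up services question:** record service type and whether the contact was planned or emergency, if the items do not already do so.
3. **SAP, safety:** tabulate emergency and inpatient contacts by level of each component.
4. **SAP, primary outcome:** keep the endpoint, and state whether emergency and inpatient care count towards it. Add one sensitivity analysis in which crisis-only contacts are not events; a participant with only such a contact stays at risk, and any later planned care counts.

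The cost is a wording amendment, at most a small addition to an existing Qualtrics question, one table and one model. The downside is a few more serious event reports and slightly fewer events in the sensitivity analysis.

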We have used a user-centered design approach to create a single chatbot prototype, which includes four key features: 1) providing a personalized recommendation for seeking intervention; 2) engaging the user in motivational interviewing to overcome barriers to care; 3) education on the seriousness and health consequences of eating disorders; and 4) repeated check-ins with the user to encourage follow-up with care.

Study 2 will use a 2⁴ full factorial trial design to test the four binary chatbot components. Thus, there are 16 experimental conditions, and participants will be randomized to 1 of those 16

conditions. Participants can be assigned to intervention ("yes") or control ("no") conditions for each chatbot component.

Participants will be recruited from those who complete the NEDA online screen and who meet eligibility criteria of screening positive for a clinical/subclinical ED, at least 18 years old, and not currently in treatment for an ED. For a period of time on the NEDA site, eligible users will be offered the chatbot. Interested individuals will be taken to a Qualtrics screen wherein those who endorse owning a smartphone and being a U.S. resident will be given access to participate in our study. Data from the NEDA eligibility screen will be collected. The consent form will be shown via Qualtrics and will encourage interested individuals to call a member of our research team to discuss the study. Once a participant completes the baseline measures, they will be randomized using Qualtrics. Once the baseline measures are completed, participants will be given information on how to access the chatbot and their unique chatbot start code.

Participants will engage with the chatbot for between 5-20 minutes, dependent on condition. Participants who are randomized to the repeated administration module will complete approximately 3 new conversations over the course of 2 weeks. The chatbot will automatically reach out to a participant if they do not complete a conversation within 1 day.

Assessments will occur online and may include data from the initial ED screen completed on the NEDA website. Assessments will take place at baseline (i.e., prior to chatbot use), and at approximately 2, 6, and 14 weeks after baseline completion via Qualtrics (see *F.2 Schedule of Measurements*).

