It is important to note that in previous similar clinical trials of digital health interventions, the procedures outlined above have been used to protect against and minimize potential risks to

participants, and they have proved effective in preventing emotional and physical complaints as well as adverse events.

E2.D. Participant Recruitment Plans and Consent Process

We plan to enroll approximately 200 English-speaking adults ≥18 years with a DSM-5 clinical or subclinical eating disorder who own a smartphone and are not in treatment for an eating disorder.

Participants will be recruited from the NEDA online screen. Once an individual screens positive for a clinical/subclinical ED, is not currently in treatment, and is ≥18 years old, they will be given a link to the Qualtrics eligibility screen. If an individual endorses owning a smartphone and being a U.S. resident, they will be shown the consent form in Qualtrics and will be asked to either agree to or decline participation in the study. Individuals will be encouraged to call a member of our research team to discuss the study.

E2.E. Randomization Method

Study 2 will use a 2⁴ full factorial trial design to test the four binary chatbot components: psychoeducation, motivational interviewing, personalized recommendations, and repeated administration. Thus, there are 16 experimental conditions, and participants will be randomized to 1 of those 16 conditions. Participants can be assigned to intervention ("yes") or control ("no") conditions for each chatbot component.

Risks

There are minimal risks for participants.

Physical Risks: N/A

Psychological Risks: Our proposed chatbot designed to facilitate mental health problems may promote increased focus on mental health symptoms in some individuals. It is also possible that participants may feel uncomfortable disclosing information about certain behaviors such as disordered eating. However, we have asked questions of a similar nature in several studies in the past and have not had participants report discomfort.

Social Risks: There may be some embarrassment related to completing questions related to disordered eating symptoms.

Financial Risks: N/A

Legal Risks: N/A

Risks to Privacy: We will go to great lengths to keep participant information private and confidential. Participant confidentiality will be maintained in compliance with HIPAA regulations.

Other Risks: N/A

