Taking part in this research study is voluntary. Participants may choose not to take part in this research study or may withdraw their consent at any time. They may withdraw by telling the research team they are no longer interested in participating in the study or they may send in a withdrawal letter. There will be no penalty or loss of benefits to which they were otherwise entitled.

E2.I. Data Collection and Follow-up for Withdrawn Subjects

When a participant withdraws from the study, the research team will stop collecting data from them.

F. Study Procedures

F1. Screening for Eligibility

Eligibility will be assessed using the NEDA eating disorder screen and eligibility questions in Qualtrics.

F2. Schedule of Measurements

Measure	NEDA Screen	Baseline Assessment	Chatbot Use	2 Week	6 Week	14 Week	Explanation/ Primary Purpose
SWED	X						To determine if the individual has a clinical/subclinical ED and to determine if they are in treatment.
Demographic Questions	x	Х					To determine if individuals are 18 years or older. To obtain demographic information for analyses.
Recruitment Rates	Х	Х					To obtain the percentage of those offered participation who enroll.
Retention Rates				X	Х	x	To obtain the percentage of follow-up completion.
Demand for Chatbot			X				Number of texts sent to the chatbot and engagement with repeated administration, if applicable.
SUS and USE				Х	Х		To examine usability of the chatbot.

Target measure: motivation for treatment and mental health services use questions	х	Х	х	х	To determine motivation for treatment and mental health services use.
Target measure: SE- KNOW	Х	Х	x	x	To determine self- efficacy in help seeking.
Target measure: personal relevance question	Х	Х	Х	х	To determine efficacy of personalized recommendation component.
Target measure: Dissonance Thermometer	Х	X	x		To determine efficacy of motivational interviewing component.
Target measure: opportunity question	X	х	Х	Х	To determine efficacy of repeated administration component.
Target measure: EDs Literacy Scale	Х	X	×	Х	To determine efficacy of psychoeducation component.
EDE-Q	Х		Х	Х	To examine ED symptoms.
EDs Quality of Life Scale	Х		Х	Х	To examine quality of life.
Patient Health Questionnaire 9	Х		х	Х	To examine depression.
Generalized Anxiety Disorder 7	Х		Х	Х	To examine anxiety.
Treatment and Barriers to Care Questions	Х		X (if no to receiving treatme nt)	X (if no to receivin g treatme	To determine any barriers to treatment utilization.

l					
ı				nt)	

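### The protocol promises evaluation of potential adverse events within 72 hours, but no planned step asks participants about them, so a low recorded count could not be told apart from under-detection

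*Combined protocol and SAP*

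**What the plan says.** Section F3, whose heading covers both data collection and reporting of adverse events, gives a definition ("adverse events will be defined as unanticipated problems involving risks to the study participants"), a time limit ("Any potentially adverse events will be evaluated by the PI within 72 hours") and reporting lines to the IRB and the mentorship team. E2.C repeats this text. Neither section says how an event comes to the PI's notice or when the 72 hours begin.

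On contact with participants, E1 states: "Assessments will occur online and may include data from the initial ED screen completed on the NEDA website". It continues: "Assessments will take place at baseline (i.e., prior to chatbot use), and at approximately 2, 6, and 14 weeks after baseline completion via Qualtrics". The F2 schedule has no row for adverse events, harms or safety at any of these times. It does list the EDE-Q, the eating disorder quality-of-life scale, PHQ-9 and GAD-7, which fall at baseline, 6 and 14 weeks as the table reads. Their stated purposes are descriptive; for PHQ-9 it is "To examine depression".

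On chatbot content, G1 states: "X2AI will host the proposed chatbot and all data collected within the chatbot". The chatbot data that E1 and F2 name for study use are the number of texts and engagement with repeated administrations.

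The SAP contains no adverse event analysis.

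**The concern.** A time limit on evaluating events works only if something brings events to the evaluator. In a remote trial nobody sees the participant, so that something has to be a question, a review of scores or text, or a report that the participant volunteers. The plan as written describes neither of the first two. The E2.C procedure for a participant who seems to be in crisis has the same dependence: someone must notice, and no means of noticing is given.

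What is at stake is the meaning of a small or zero count. The Risks text acknowledges that the chatbot could increase some users' focus on their symptoms. It then draws reassurance from participants in earlier studies not having reported discomfort, and E2.C says that the same procedures prevented complaints and adverse events in similar trials. An absence of reports supports such a statement only when it is known that people were asked.

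**Working it through.** The documents give no expected adverse event rate and no safety precision, so there is no stated figure to reproduce. The check has two parts.

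**1. Possible routes by which an event could reach the PI**

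| Route | What the documents provide | Stated link to adverse event review |
|---|---|---|
| 2-, 6- and 14-week assessments (E1, F2) | Online questionnaires; no adverse event row | None |
| EDE-Q, quality of life, PHQ-9, GAD-7 (F2) | Baseline, 6 and 14 weeks as the table reads; not at 2 weeks, about when chatbot use ends | None: no worsening threshold and no review step |
| Chatbot text (E1, F2, G1) | Hosted by the vendor; number of texts and engagement named for study use | Not addressed |
| Validation of treatment receipt (E1) | Staff "contact a random subset of participants (i.e., approximately 10%) who reported engaging in some kind of treatment" | None; the purpose is to confirm service use |
| Reminders (E1) | Email, phone and/or text | None; any disclosure is incidental |
| Volunteered report (E2.C) | Participants receive staff contact details | Implied |
| Withdrawal (E2.C, F3) | An explanation goes to the mentorship team; E2.I then ends data collection | Yes, for withdrawals only |

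No row is a planned enquiry about adverse events. What remains is volunteered reports, withdrawal explanations and incidental contact.

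**2. What a low count could mean**

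Inputs:
- n = 200, from E2.D: "We plan to enroll approximately 200 English-speaking adults".
- s, the share of affected participants whose event reaches the team. This is an assumption, shown from 5% to 100%.
- p, the true proportion of participants with an event. This is an assumption, with 1%, 5% and 10% used for illustration.

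If capture is independent between participants, the number recorded is Binomial(200, p × s).

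With 0 recorded, the one-sided 95% upper limit solves (1 − p × s)^200 = 0.05, so p = [1 − 0.05^(1/200)] / s = 0.01487 / s.

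| Capture s | Upper limit for p, 0 recorded |
|---|---|
| 100% | 1.5% |
| 50% | 3.0% |
| 25% | 5.9% |
| 10% | 14.9% |
| 5% | 29.7% |

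Probabilities of a low count when p = 5% (200 × 0.05 = 10 affected participants expected):

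| Capture s | Expected recorded, 200 × p × s | P(0) | P(2 or fewer) |
|---|---|---|---|
| 100% | 10 | <0.001 | 0.002 |
| 25% | 2.5 | 0.08 | 0.54 |
| 10% | 1 | 0.37 | 0.92 |

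The data cannot separate p from s. A true 1% with full capture and a true 10% with 10% capture both give p × s = 0.01. Each implies 200 × 0.01 = 2 expected records and a probability of 0.68 of recording 2 or fewer. The recorded counts have the same distribution in both cases.

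**The case against.** The strongest reply has four parts.

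- **Harm is partly measured.** Depression, anxiety, eating disorder symptoms and quality of life are asked about systematically and can be compared by randomised component. This stands as far as it goes: deterioration on those scales would be in the data. But nothing sends a worsening score to the PI within 72 hours or at all, and an event outside those scales would not appear.
- **The detail may exist elsewhere.** The protocol refers to a Data and Safety Monitoring Plan but gives little beyond monitoring by the PI and mentors. Questionnaire items are not reproduced, and the consent form is not available to this review. This stands, and the conclusion is conditional on it. If a procedure exists, F3 should state or cite it.
- **The definition is narrow and the intervention brief.** Adverse events are limited to unanticipated problems, and chatbot use is 5 to 20 minutes depending on condition, so the true rate may well be low. That is possible. But unanticipated problems cannot be listed in advance, which favours an open question.
- **An open question will collect much that is not an adverse event.** This stands as a cost.

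Four stronger readings are tempting, but the documents do not support them:

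- A reader might infer that a safety conclusion will be carried into the R01 trial. F4 says the R01 is to be informed by feasibility and component effect sizes, and the SAP plans no adverse event count.
- A reader might infer that spontaneous counts would differ between components because longer chatbot contact gives more chance to disclose. That requires chatbot text to reach the team, which no section describes, and extra conversations are described only for repeated administration.
- A reader might infer that vendor hosting puts the text out of the team's reach. The documents are silent on access; some chatbot data evidently do reach the study, and a Business Associate agreement is in place.
- A reader might infer that the 72-hour rule or the crisis procedure contradicts another section. Both are conditional procedures; the plan is incomplete here, not inconsistent.

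**Conclusion.** The concern holds as a gap in ascertainment. The plan commits to evaluating events promptly without describing a step that finds them, so a low recorded count could not be told apart from under-detection. It does not follow that events will be common or that a low count would be wrong; a truly low rate is equally compatible with the plan.

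The gap is more than missing wording, because closing it changes what is collected. It does not affect the primary analyses. The upper limits of 1.5% to 29.7% for a zero count show how far interpretation depends on capture; they are not estimates. They rest on 200 participants, independent capture and assumed capture shares, and the conclusion as a whole assumes that no detection procedure sits in the unreproduced monitoring plan or questionnaires.

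**What to change.** - Add one open question to the existing 2-, 6- and 14-week Qualtrics assessments, asking about unexpected or worsened problems since the last assessment, with a free-text box.
- Have a response notify the study team automatically, and state in F3 that this notification starts the 72-hour evaluation. The PI then applies the protocol's own adverse event definition, which need not change.
- Add a row to F2, and a line to the SAP tabulating events descriptively by component with the number who answered the question. If allocation is balanced, each component level has about 200 / 2 = 100 participants, and 0 of 100 gives an upper limit of 1 − 0.05^(1/100) = 3.0% even at full capture, so no formal comparison is warranted.
- State whether and how safety concerns appearing in chatbot text reach the study team.
- If the Data and Safety Monitoring Plan already provides a procedure, cite it in F3.

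The cost is one item at three existing assessments (at most 200 × 3 = 600 responses), a notification setting and protocol wording, with no added visits. The downside is more minor reports for the PI to review. The question will not reach people who skip an assessment or withdraw, so capture will still be incomplete, but the number asked and the number answering will be known.
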